In a recently published single center study of 115 participants, 53 were Uphold® hysteropexy procedures³² at a median follow-up of 11.8 months (range 0.4-30.9 months). Using POP-Q ≥ -1 to define recurrence, the combined anterior apical recurrence rate was 1.89%, including no anterior ($Ba \geq -1$) and one apical ($C \geq -1$). Using POPQ ≥ 0 there were no recurrences in $Ba \geq 0$ or $C \geq 0$ compartment. The mesh exposure rate was 1.9%. In the overall group of 115 participants, 13.4% (13/97) reported preoperative dyspareunia and 8.3% reported postoperative dyspareunia (8/97). Dyspareunia resolved in 12/13 with preoperative dyspareunia and was de novo in 6 participants – all 6 had perineorrhaphy. As noted earlier, over 15,000 Uphold® kits have been sold in the U.S. (personal communication 5/2011) but their usage for uterine prolapse vs. vault prolapse indications is not known. However, this number would make it significantly more common than any suture/native tissue/ligament hysteropexy technique. A

Confidential Please Do Not Copy

recent study of 31 women randomized to hysterectomy or hysteropexy, both using polypropylene mesh, found no significant differences in outcomes.^{33, 34}

A review of clinicaltrials.gov reveals that there are 2 ongoing registered trials studying the Uphold® procedure as a hysteropexy:

1. VAULT study (<http://clinicaltrials.gov/ct2/show/NCT01377142?term=Vault&rank=1>): “Vaginal Uphold Hysteropexy and Laparoscopic Sacral Hysteropexy for the Treatment of Uterovaginal Pelvic Organ Prolapse (VAULT)”. This multicenter trial is sponsored by the Foundation for Female Health Awareness and coordinated at the Cleveland Clinic with anticipated enrollment that will end in summer 2012. This study is not randomized and has a one-year outcome. Both groups retain their entire uteruses and the primary outcome is a composite outcome including cervix above the mid-vagina, absence of any prolapse beyond the hymen, absence of retreatment and absence of vaginal bulge symptoms. Secondary outcome measures include anatomic, symptomatic, short-term morbidity, pain and functional activity.

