Postoperative recovery#			X										
POPQ	X			X	X	X	X	X	X	X	X	X	X
AE review		X	X	X	X	X	X	X	X	X	X	X	X
Exam for mesh exposure			X	X	X	X	X	X	X	X	X	X	X
PFDI – Question 3	X		X	X	X	X	X	X	X	X	X	X	X
Functional Activity Scale	X		X	X	X	X	X		X		X		X
Surgical Pain Scale	X		X	X	X	X	X		X		X		X
PFDI-20 (includes POPDI-6, CRADI-8, UDI-6)	X		X	X	X	X	X		X		X		X
PFIQ	X			X	X	X	X		X		X		X
PGI-I				X	X	X	X		X		X		X
ISI	X		X	X	X	X	X		X		X		X
PISQ-IR	X			X	X	X	X		X		X		X
BIS	X		X	X	X	X	X		X		X		X
SF-12	X			X	X	X	X		X		X		X

* Includes OR complications with Dindo score, EBL, Transfusion, HGB change from pre-op to POD1, length of hospital stay.

Assess duration of postoperative catheterization, PVR, de novo incontinence, pelvic pain scale and pain mapping review for vagina, groin, and leg pain.

M. Outcome Measures

The following outcome measures will be collected at baseline, 6 months, 12 months, and then every 6 months with the survival analysis approach.

M.1 Primary Outcome Measure

A participant will be considered a treatment failure if any ONE of the following criteria is met:

- 1) Report of bothersome vaginal bulge symptoms (see definition below), or
- 2) Re-treatment for prolapse (surgery or pessary), or

Confidential Please Do Not Copy

- 3) Any prolapse measure (Ba, C, Bp) is beyond the hymen (i.e. > 0 cm)

Bothersome vaginal bulge symptoms = positive response to Question 3 of the PFDI-20: “Do you usually have a bulge or something falling out that you can see or feel in your vaginal area?” AND any degree of bother. This single question has been identified to most accurately and reliably identify those women with POP. An affirmative answer to this question was 96% sensitive (95%CI 92-100) and 79% specific (95%CI 77-92) for prolapse beyond the hymen. The 1-week test-retest reliability was good (kappa .84).⁴⁷

Participants not considered a treatment failure for the primary outcome will be considered a treatment success.

M.2 Comparative Secondary Outcome Measures

Secondary Aim 1 – Secondary Efficacy Outcomes: These measures will require a statistical analysis plan and will be reported in the primary outcome manuscript.

- 1) Anatomic: POPQ point (Ba, Bp, C), mean or median (but should be normally distributed) measures postop in each group. Proportion of participants in each group with C > -1/2 TVL.
- 2) Functional:
 - a) Prolapse – mean Patients Global Impression of Improvement (PGI-I)⁴⁸, mean overall prolapse symptoms using POPDI-6⁴⁹ scores

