This study is designed to compare the relative effectiveness of two transvaginal apical suspension strategies for uterovaginal prolapse: a mesh augmented hysteropexy vs. vaginal hysterectomy and uterosacral ligament suspension. Power and sample size calculations were generated to determine the sample size needed to test for treatment difference favoring the mesh augmented strategy (i.e., a superiority trial) across the study arms for a variety of assumptions about effect size and study follow-up time. For all power analyses, we assumed that failure in both arms follows an exponential survival model and that the native tissue repair has a success rate of 80% at 24 months. This 80% calculation is based on an assumed 85% anatomic success rate for uterosacral ligament suspension (Table 2) and an additional 5% failure rate based on symptom failure. In the only published Uphold® series there is a 98% 12 month anatomic success rate.³² Although no 2-year outcome data are available for the Uphold® procedure, under an assumption of a constant hazard, the 1-year success rate of 98% yields an estimated 2-year anatomic success rate of 96%; combining this estimate with a similar 5% rate for symptom failure yields a 91% composite (anatomic and symptom) success rate. All analyses also assumed that statistical tests would be conducted with a Type I error rate of 0.05 with adjustment for multiple comparisons based on a single interim analysis. Sample size estimates assumed that the 2-year success rate in the mesh-augmented arm is in the range of 90% to 93% at 24 months (note that this represents a hazard ratio in the range of 0.33 to 0.47 under the assumed exponential survival model), that the enrollment time for the study is 2 years, the loss-to-follow-up on both arms is no more than 5% per year, and the total study duration from last participant enrolled to primary outcome analysis is 36 months with one interim analyses for efficacy when the last participant reaches the 24-month follow-up. Table 7 provides estimates of the power for the different assumptions for total sample sizes in the range of 160 to 300 participants under the assumption that a single interim analysis will be conducted using O’Brien-Fleming stopping rules.

Table 7. Sample Size Calculations

Total Sample Size	Power as a Function of 2-Year Effect Size—with Base 2-Year Success of 80% and 36-Month Follow-Up After Last Enrollment and a 2-Year Enrollment Period			

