6 SAMPLE SIZE DETERMINATION

This study is designed to compare the relative effectiveness of two transvaginal apical suspension strategies for uterovaginal prolapse: a mesh augmented hysteropexy vs. vaginal hysterectomy and uterosacral ligament suspension. Power and sample size calculations were generated to determine the sample size needed to test for treatment difference favoring the mesh augmented strategy (i.e., a superiority trial) across the study arms for a variety of assumptions about effect size and study followup time. For all power analyses, we assumed that failure in both arms follows an exponential survival model and that the native tissue repair has a success rate of 80% at 24 months. This 80% calculation is based on an assumed 85% anatomic success rate for uterosacral ligament suspension (Table 2) and an additional 5% failure rate based on symptom failure. In the only published Uphold series there is a 98 % 12 month anatomic success rate.32 Although no 2-year outcome data are available for the UPHOLD procedure, under an assumption of a constant hazard, the 1-year success rate of 98% yields an estimated 2-year anatomic success rate of 96%; combining this estimate with a similar 5% rate for symptom failure yields a 91% composite (anatomic and symptom) success rate. All analyses also assumed that statistical tests would be conducted with a Type I error rate of 0.05 with no adjustment for multiple comparisons. Sample size estimates assumed that the 2-year success rate in the meshaugmented arm is in the range of 90% to 93% at 24 months (note that this represents a hazard ratio in the range of 0.33 to 0.47 under the assumed exponential survival model), that the enrollment time for the study is 2 years, the loss-to-follow-up on both arms is no more than 5% per year, and the total study duration from last participant enrolled to stopping the study for final analysis is 36 months with one interim analyses for efficacy when the last participant reaches the 24-month follow-up. Table 6 provides estimates of the power for the different assumptions for total sample sizes in the range of 160 to 300 participants.

Total Sample Size	Power as a Function of 2-Year Effect Size—with base 2-Year Success of 80% and 36-Month Follow-up after last enrollment and a 2-year Enrollment Period						
	∆= 0.10 HR=0.472	Δ=0.11 HR=0.423	Δ=0.12 HR=0.374	∆=0.13 HR=0.325			
160	0.87	0.93	0.96	0.99			
180	0.89	0.95	0.98	0.99			
200	0.92	0.96	0.99	>0.99			

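### The mesh-arm planning rate omits the posterior wall and uses a different anatomic threshold, so it is not on the same basis as the control rate or the primary outcome

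*Protocol*

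**What the plan says.** **Mesh arm.** Protocol Section N states: "In the only published Uphold® series there is a 98% 12 month anatomic success rate". It squares this under a constant hazard to reach 96% at two years. It then subtracts symptom failure, and SAP Section 6 repeats the step: "combining this estimate with a similar 5% rate for symptom failure yields a 91% composite (anatomic and symptom) success rate".

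**Source of the 98%.** Protocol B.1, under the mesh strap hysteropexy heading, describes the series. The threshold is given as "Using POP-Q ≥ -1 to define recurrence", and the result is that "the combined anterior apical recurrence rate was 1.89%, including no anterior" failure and one apical failure occurred. Follow-up is reported "at a median follow-up of 11.8 months (range 0.4-30.9 months"). The same paragraph says there was no Ba or C recurrence at POPQ ≥ 0. It gives no Bp result.

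**Control arm.** Section N says: "This 80% calculation is based on an assumed 85% anatomic success rate for uterosacral ligament suspension (Table 2"). The success column of Table 2 covers all segments, and its recurrence column lists posterior recurrences.

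**Endpoint.** Protocol M.1 (repeated in SAP 3.2) counts as failure: "Any prolapse measure (Ba, C, Bp) is beyond the hymen (i.e. > 0 cm").

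**The concern.** In a time-to-event design the two assumed success rates set both the hazard ratio and the expected number of failures, so they should measure the same thing, and that thing should be the endpoint. Here they do not. The mesh rate leaves out one of the three compartments. The control rate and the endpoint include it.

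Nothing in the plan explains why posterior failure should be absent in the mesh arm. Protocol B.1 and J.2 allow posterior colporrhaphy at the surgeon's discretion in both arms, and the mesh is placed through an anterior incision.

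The 98% is also a crude proportion at a median of 11.8 months with follow-up as short as 0.4 months. About half the women had been followed for less than a year, yet the figure is treated as a 12-month rate and extrapolated to 24 months.

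At stake is how a non-significant result is read. SAP 7.4 says the comparison matters for public health even if no efficacy difference is shown, so readers need to know which differences 180 women could have detected.

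**Working it through.** **1. Reproduce the planning rates.**
- Mesh: 1/53 = 1.89%, so success is 98.1%. Then 0.98² = 0.960, and 0.96 − 0.05 = 0.91.
- Control: 0.85 − 0.05 = 0.80.
- Difference: 11 points. The derivation reproduces, and it confirms that the 98% is the anterior-apical figure.
- The exact 95% interval for 1/53 is 0.05% to 10.1%.

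**2. Check that 85% behaves as an all-segment rate.** The ten success rates in Table 2 have an unweighted mean of 84.5%. Without the two rows defined on the apex or vault alone, the mean is 85.0%.

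**3. Set the three definitions side by side.**

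| | Compartments | Threshold for failure | Time |
|---|---|---|---|
| Mesh 98% | Ba, C | ≥ -1 | crude, median 11.8 months |
| Control 85% | all segments | mixed; success is grade or stage 0–1 in six of eleven rows | mixed; stated means 12 to 61.2 months |
| Primary outcome | Ba, C, Bp | > 0 cm | time to failure |

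**4. Power as a function of an assumed posterior failure rate p.** The inputs, from Protocol A.1 and N, are: 180 women 1:1, two-sided 0.05, exponential failure, control success 0.80 at 24 months, uniform 24-month accrual, 36 months after the last enrolment, and 5% annual loss. Mesh success is 0.91 − p.

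- Monthly hazards: λ = −ln(S24)/24; loss g = −ln(0.95)/12.
- Event probability per arm: the average of λ/(λ+g) × [1 − exp(−(λ+g)u)] over u from 36 to 60 months.
- Expected failures D = 90 × (sum of the two probabilities).
- Power = Φ(|ln HR| × √D / 2 − 1.96).

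Worked case, p = 0. The event probabilities are 0.326 (control) and 0.155 (mesh), so D = 43.4. HR = ln(0.91)/ln(0.80) = 0.423 and |ln HR| = 0.861. Then 0.861 × √43.4 / 2 − 1.96 = 0.88, and power is 0.81.

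| p | Mesh success | Difference (points) | HR | D | Power |
|---|---|---|---|---|---|
| 0 | 91% | 11 | 0.423 | 43.4 | 0.81 |
| 1% | 90% | 10 | 0.472 | 44.8 | 0.71 |
| 1.4% | 89.6% | 9.6 | 0.492 | 45.4 | 0.67 |
| 3% | 88% | 8 | 0.573 | 47.7 | 0.49 |
| 5% | 86% | 6 | 0.676 | 50.6 | 0.29 |

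A log-rank simulation with the same inputs gives 0.79 at 91%, 0.69 at 90%, 0.65 at 89.6% and 0.28 at 86%. Power reaches 0.80 at a mesh success of 90.9%.

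The values of p are assumptions, because the documents give no posterior rate for the device. Table 2 reports posterior recurrence after uterosacral suspension of 1.4%, 5%, 12%, 14% and 14.6%.

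**5. Relation to Table 7.** Protocol Table 7 gives 0.89 and 0.95 for 10 and 11 points at N = 180. The formula above gives 0.71 and 0.81. That gap exists at p = 0 and is a separate matter from the compartment mismatch. The rows of step 4 should be compared with each other and not with Table 7.

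**The case against.** A reader might infer that the 11-point effect is overstated, and that the real power lies somewhere around 0.24 to 0.67. The documents do not support either statement, for four reasons.

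- **Threshold.** The 1.89% uses ≥ -1, which is stricter than the trial's > 0 cm, and the series had no Ba or C recurrence at ≥ 0. If the mesh arm alone were moved to that basis, its composite would be 100% − 5% = 95% before any posterior allowance, and the gap would fall below 11 points only if p exceeded 4%. This stands, but it is not a full answer, because the control would move too. Mesh anatomic success can rise by at most 4 points (96% to 100%), whereas the control's 85% has up to 15 points of room.
- **Borrowed rates.** The Table 2 posterior figures come from native-tissue series with follow-up of 12 to 61.2 months, or not stated, and with mixed definitions. The size-weighted mean of the five rates, 5.6%, gives the 0.24, but one series supplies 289 of the 488 women behind it. It is a mean and not an upper limit; the rates run to 14.6%.
- **Overlap.** The 5% symptom allowance may already contain some posterior failures, since M.1 reports 96% sensitivity of the bulge question for prolapse beyond the hymen.
- **Planning range.** The plan starts at 10 points, so p up to 1% stays inside it. From 10 points, p = 1.4% takes power from 0.71 to 0.67, a loss of about 4 points.

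It is also fair to say that interval estimates of the arm-specific rates are planned (Protocol O, SAP 9.3), which limits the risk that a null result is read as no difference.

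None of this removes the mismatch. The 98% is still described as something it is not.

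**Conclusion.** The concern holds as a mismatch of basis. The mesh planning rate is a crude anterior-apical rate at ≥ -1 from 53 women at a median of 11.8 months. The control rate covers all segments, and the endpoint covers Ba, C and Bp beyond the hymen. At the grade or stage 0–1 threshold used in six of the eleven Table 2 rows, the omission can only favour mesh. At the hymen threshold, whether the 11 points are too many or too few cannot be settled from the documents.

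Power is sensitive to the missing compartment: within one method it falls from 0.81 to 0.67 at p = 1.4% and to 0.29 at p = 5%. These values assume that posterior failures add to those already counted and that the control stays at 80%. Overlap with the symptom allowance, or the looser hymen threshold, would reduce the loss. With 80% control success, 80% power needs mesh success of about 91%, so a null result would not exclude smaller differences.

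**What to change.** In Protocol N and SAP 6:

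1. Describe the 98% as Ba and C only, at POP-Q ≥ -1, 1 of 53 women, median 11.8 months, exact 95% interval for recurrence 0.05% to 10.1%. Stop calling it 12-month anatomic success.
2. Add a labelled sensitivity analysis that subtracts an assumed mesh-arm posterior failure p, with the power figures tabulated above. Say that no posterior rate for the device is available, that the Table 2 rates run from 1.4% to 14.6%, and that overlap or the hymen threshold would reduce the loss.
3. State that 80% power requires mesh success of about 91% when control success is 80%, so a non-significant result leaves smaller differences open.
4. Reconcile these figures with Table 7, whose 0.89 and 0.95 do not reproduce from the stated inputs. Otherwise the section would carry two incompatible sets of power values. SAP 6 also needs its text (0.99 for 11 points) matched to its own table (0.95).

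The cost is a few sentences and one small table. The sample size stays at 180, with no added patients, visits or procedures. The downside is a less favourable stated power.

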Table 1. Vaginal Surgery Treatment Options for Uterovaginal Prolapse (non-obliterated procedures only)	2
Table 2. Uterosacral Vault Suspension Procedures	3
Table 3. Masking Summary	20
Table 4. Timeline of Measures	22
Table 5. Resource Utilization Data Collection and Price Data Source, by Utilization Category	26
Table 6. Body Image Scales	29
Table 7. Sample Size Calculations	30

A. Study Aims

The primary purpose of this randomized clinical trial is to compare the effectiveness and safety of two transvaginal apical suspension strategies for uterovaginal prolapse: a mesh augmented hysteropexy vs. vaginal hysterectomy and uterosacral ligament suspension.

A.1 Primary Aim

1. To determine whether treatment success in women with symptomatic uterovaginal prolapse undergoing transvaginal mesh augmented hysteropexy differs in women undergoing vaginal hysterectomy and native tissue cuff suspension at time points through 3 years.

Hypothesis –

1. This study will test the null hypothesis that treatment success will not differ in women with symptomatic uterovaginal prolapse undergoing vaginal surgery with a synthetic mesh hysteropexy compared to women undergoing vaginal hysterectomy with native tissue vaginal suspension against the alternative hypothesis that success does differ for the treatment regimens. Operationally, the hypothesis will be tested using a two-sided log-rank test to test for a difference in the risk of failure across the two treatment arms to achieve an overall Type I error rate of 0.05 across the interim and final analyses.

A.2 Secondary Aims

1. **Secondary Efficacy Outcomes:** To compare detailed anatomic and comprehensive functional outcomes (including prolapse, urinary, sexual, bowel and health-related quality of life (HRQOL)) in both groups.
2. **Safety:** To measure and compare safety, adverse events (including mesh erosion and exposure), pain, and need for subsequent procedures in both groups.
3. **Predictors of Poor Outcomes:** To determine if advanced prolapse, age, obesity, smoking, menopausal status, estrogens, previous prolapse surgery, and physical activity levels, alone or in combination, predict higher treatment failure.
4. **Cost-Effectiveness:** To compare the cost-effectiveness of the two surgical approaches and relate the difference in cost of care between the two groups to differences in health utilities and health-related quality of life.

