	$\Delta=0.10$ HR=0.472	$\Delta=0.11$ HR=0.423	$\Delta=0.12$ HR=0.374	$\Delta=0.13$ HR=0.325
160	0.87	0.93	0.96	0.99
180	0.89	0.95	0.98	0.99
200	0.92	0.96	0.99	>0.99
220	0.94	0.98	0.99	>0.99
240	0.96	0.98	0.99	>0.99
260	0.95	0.99	0.99	>0.99
280	0.98	0.99	>0.99	>0.99
300	0.98	0.99	>0.99	>0.99

Based on these calculations, a total of 180 participants will be randomized at a 1:1 ratio to the two treatment arms. This sample size will provide a power of 0.89 to detect an additive difference of 10% in the 2-year success rate (i.e. a hazard ration of 0.472) and a power of 0.95

Confidential Please Do Not Copy

to detect additive differences of 11% or greater in the 2-year success rate (hazard ratios of 0.423 or less).

One of the advantages of the survival analysis approach is that the study continues to accumulate information on individuals enrolled early in the study as they have events beyond a fixed two-year or three-year time frame, particularly for a study like this one in which successes are more likely to occur than are failures over the first three years. As such, the survival approach with multiple looks will allow the analysis of the primary outcome of overall risk of treatment failure for the study to be completed and results published, while still collecting information on longer-term outcomes.

O. Statistical Design

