220	0.94	0.98	0.99	>0.99			
240	0.96	0.98	0.99	>0.99			
260	0.95	0.99	0.99	>0.99			
280	0.98	0.99	>0.99	>0.99			
300	0.98	0.99	>0.99	>0.99			

Based on these calculations, a total of 180 participants will be randomized at a 1:1 ratio to the two treatment arms. This sample size will provide a power of 0.89 to detect an additive difference of 10% in the 2-year success rate (i.e. a hazard ration 0f 0.472) and a power of 0.99 to detect additive differences of 11% or greater in the 2-year success rate (hazard ratios of 0.423 or less).

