The first two sections below describe a modified analytic approach that treat participants in a manner consistent with the original analysis design in that study participants that meet the criteria for treatment failure a remain treatment failures until they are lost to follow-up or the study ends. The proposed model-based and nonparametric analytic methods address interval censoring and non-proportional hazards in the assessment of the study's primary hypothesis. The model-based approach will serve as the primary analytic method for testing the efficacy of the two strategies for uterovaginal prolapse as it can control for study design and potentially confounding variables, while the nonparametric method will serve a confirmatory role, particularly in the masked analysis as detailed below. The third section focuses on modeling recurrent events to better understand the impact of the interventions over time. The analytic methods for estimating survival curves will first be conducted in a blinded fashion on all subjects, ignoring treatment assignment as a part of a masked analysis, then comparing subjects randomized their interventions in an unmasked analysis.

Model-based analysis:

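### With 180 women the plan's own inputs give power of about 0.64–0.75 at a 10-point 2-year difference and 0.74–0.85 at 11 points, not the stated 0.89 and 0.95 (0.99 in the SAP sentence)

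*Protocol*

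**What the plan says.** Protocol Section N bases the choice of 180 women on Table 7. The table is described as running "for total sample sizes in the range of 160 to 300 participants", and its first column is headed as a total. For N=180 it prints power of 0.89, 0.95, 0.98 and 0.99 at 2-year differences of 10, 11, 12 and 13 points. The text says: "This sample size will provide a power of 0.89 to detect an additive difference of 10% in the 2-year success rate".

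The inputs given there are exponential failure in both arms, 80% control success at 24 months, 90–93% in the mesh arm, 2-year enrolment, 36 months from last enrolment to the primary analysis, and "the loss-to-follow-up on both arms is no more than 5% per year". The error rate is described as a "Type I error rate of 0.05 with adjustment for multiple comparisons based on a single interim analysis". Protocol A.1 supplies the test: "the hypothesis will be tested using a two-sided log-rank test".

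SAP Section 6 prints the same table but differs in two ways. It describes a "Type I error rate of 0.05 with no adjustment for multiple comparisons", and its closing sentence claims "a power of 0.99 to detect additive differences of 11% or greater in the 2-year success rate", although the N=180 row above it shows 0.95. SAP 9.3 later replaces the log-rank test: "The model-based approach will serve as the primary analytic method". The power section was not revisited for that change.

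**The concern.** A quick event count raises the doubt. Two-sided power of 0.89 at a hazard ratio of 0.472 needs more than 70 failures. In 180 women with 10–20% failing by two years and 3–5 years of follow-up, fewer than 50 are expected. The table also has visible faults: at 10 points, power falls from 0.96 at N=240 to 0.95 at N=260, and one set of figures is described as both adjusted and unadjusted for the interim.

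The sample size is justified by these figures, and SAP Section 2 sends the results to the primary manuscript and to the manufacturer's FDA report. A reader of a non-significant result would take the trial as having 89–99% power at 10–11 points. The interval estimates the plan requires will show what a null result excludes, but the quoted power would mislead anyone relying on it.

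**Working it through.** **Inputs.** From Protocol N: N=180 in total, 1:1, so 90 per arm; 24-month success 0.80 in control and 0.90, 0.91, 0.92 or 0.93 in mesh; 2-year enrolment plus 36 months; loss of no more than 5% a year. From A.1: two-sided test. Assumed: uniform accrual, so follow-up is uniform on 3–5 years, and exponential loss. Loss is shown at 0 and 5%.

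**Hazard ratios.** These reproduce. ln(0.90)/ln(0.80) = 0.10536/0.22314 = 0.472, and likewise 0.423, 0.374 and 0.325, as printed.

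**Expected failures at 10 points.** Yearly hazards are λ = −ln(0.80)/2 = 0.1116 (control) and −ln(0.90)/2 = 0.0527 (mesh). The loss hazard is μ = −ln(0.95) = 0.0513, or 0. Failures per arm are

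90 × λ/(λ+μ) × {1 − [e^(−3(λ+μ)) − e^(−5(λ+μ))]/[2(λ+μ)]}.

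- No loss: 32.3 + 17.1 = 49.3 (unrounded sum).
- 5% loss: 29.4 + 15.5 = 44.8 (unrounded sum).

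At 11 points the totals are 47.7 and 43.4.

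**Power at 10 points.**

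- Schoenfeld, Φ(√(D/4)·|ln HR| − 1.96), with |ln HR| = 0.750: Φ(3.348 × 0.750 − 1.96) = 0.71 with 5% loss; Φ(3.512 × 0.750 − 1.96) = 0.75 with none.
- Freedman, Φ(√D·(1−HR)/(1+HR) − 1.96), with (1−HR)/(1+HR) = 0.3585: 0.67 with 5% loss; 0.71 with none.

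**All four columns at N=180, two-sided.** The log-rank rows are simulations of 8,000 trials per cell with a Lan-DeMets O'Brien-Fleming interim. The piecewise exponential rows use 2,500 trials per cell, with the SAP 9.3 periods and 8 equal sites as fixed effects.

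| Method | 10 | 11 | 12 | 13 |
|---|---|---|---|---|
| **Stated (Table 7)** | 0.89 | 0.95 | 0.98 | 0.99 |
| Schoenfeld, no loss | 0.75 | 0.845 | 0.92 | 0.96 |
| Schoenfeld, 5% loss | 0.71 | 0.81 | 0.89 | 0.95 |
| Freedman, no loss | 0.71 | 0.80 | 0.87 | 0.92 |
| Freedman, 5% loss | 0.67 | 0.76 | 0.84 | 0.90 |
| Log-rank, no loss | 0.71–0.72 | 0.80–0.82 | 0.87–0.89 | 0.94 |
| Log-rank, 5% loss, exact times | 0.68 | 0.78 | 0.86 | 0.93 |
| Log-rank, 5% loss, 6-monthly detection | 0.65 | 0.75 | 0.84 | 0.90 |
| Piecewise exponential, no loss | 0.70–0.74 | 0.80–0.83 | 0.88–0.90 | 0.93–0.95 |
| Piecewise exponential, 5% loss, exact times | 0.70 | 0.81 | 0.88 | 0.92 |
| Piecewise exponential, 5% loss, 6-monthly | 0.65 | 0.75 | 0.83 | 0.89 |
| Same, tested at 0.047 | 0.64 | 0.74 | 0.83 | 0.89 |

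**Does the interim explain the gap?** No. Simulated log-rank power at 10 points with 5% loss and exact times is 0.689 without the interim and 0.681 with it.

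**Do relaxed inputs restore 0.89 at 10 points (Schoenfeld)?**

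- 60 months for every woman: 0.78 with 5% loss, 0.82 with none.
- One-sided 0.05 on the stated schedule: 0.81 with 5% loss, 0.84 with none.
- 180 per arm on the stated schedule with 5% loss: 0.94. This exceeds 0.89 but contradicts a total of 180.

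**What reproduces the printed table?** More than one set of unstated inputs does, over all 32 cells (entries above 0.99 read as 0.995):

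- One-sided 0.05, 5 years for everyone, no loss: N=180 row 0.893/0.947/0.978/0.993; mean absolute difference 0.0041.
- Two-sided, N per arm, 3 years each, 5% loss: 0.890/0.949/0.981/0.995; mean absolute difference 0.0047.
- The stated inputs: mean absolute difference 0.076.

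The origin of the table therefore cannot be settled from the documents.

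**Scale.** Power of 0.89 at 10 points needs 72 failures (Schoenfeld) or 79 (Freedman). At 0.274 failures per woman without loss, or 0.249 with 5% loss, that is 72.1/0.274 = 263 to 79.0/0.249 = 317 women. The SAP's 0.99 at 11 points needs about 99 failures; 43–48 are expected.

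**The case against.** The strongest objection is that nothing now turns on the figure. Protocol Amendment T puts the last randomization in January 2015, SAP 4.4.2 sets the first data lock at visits to February 2018, and SAP 7.4 restricts futility to enrolment. A recomputed table changes no decision. That is true, and it is why the remedy is confined to text; it does not make the printed power correct.

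Four further points have some force:

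- **The relevant column is 11 points.** The plan's own projection is 91% against 80%. Power there is better, at 0.74–0.85, but still well below 0.95 and 0.99.
- **5% loss is a ceiling.** Amendment U reports three-year outcome data for 96% of women. Read as about 1.4% annual loss (an assumption; 1 − 0.96^(1/3)), Schoenfeld and Freedman give 0.74 and 0.70 at 10 points, and 0.835 and 0.79 at 11. The upper part of the range is then the more realistic, but the conclusion is the same.
- **Section N words the calculation as favouring mesh**, which could mean a one-sided test. The declared test is two-sided in A.1, Section O and SAP 3.1.1, and one-sided power on the stated schedule reaches at most 0.84 at 10 points.
- **The piecewise exponential runs approximate the SAP model.** They set the random-intercept variance to zero, and null rejection ran from 0.050 to 0.059. They show that the change of primary method is unlikely to rescue the figure. The finding does not depend on them.

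**Conclusion.** The stated power is wrong as written. On the plan's own two-sided design with 180 women in total, power is about 0.64–0.75 at 10 points against 0.89, and 0.74–0.85 at 11 points against 0.95 in the table and 0.99 in the SAP sentence. The shortfall at 10 points is 14–25 percentage points, and the type II error there is about 0.25–0.36 instead of 0.11. This rests on uniform accrual and annual loss of 0–5%. Accrual pattern is not decisive, since five years for every woman with no loss still gives only 0.82.

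Three faults need no modelling: the SAP's 0.99 contradicts its own row, the N=260 cell is below N=240, and identical figures are described as both adjusted and unadjusted for the interim. The interim conflict is small in effect (about 0.01), but both descriptions cannot be right.

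**What to change.** Keep N=180. Recompute Table 7 and the summary sentences in Protocol N and SAP 6 for a two-sided 0.05 test with the interim, staggered 3–5 year follow-up and annual loss of 0–5%, and name the method. A suitable sentence would be:

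> With 180 women in total, power is approximately 0.65–0.75, 0.75–0.85, 0.84–0.92 and 0.90–0.96 for 2-year differences of 10, 11, 12 and 13 points. The lower end is a simulated log-rank test with 6-monthly detection, the interim and 5% annual loss; the upper end is Schoenfeld's formula with no loss, before about 0.01 for the interim. These are log-rank design approximations; the primary analysis is the site-adjusted piecewise exponential model of SAP 9.3.

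Quoting a single method at 0 and 5% loss would be tidier and equally acceptable.

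Also delete the SAP's 0.99 at 11 points, recompute the N=260 cell, and make Protocol N and SAP 6 agree on interim adjustment. SAP Section 14 is still to be completed and can record the correction.

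The cost is a recomputed table, some wording, and a less favourable stated power. It needs no extra participants and no change to alpha or analysis.
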